## 9.5 POST-TRANSPLANT STANDARD OF CARE CONCOMITANT MEDS

Patients are recommended to be on ursodiol (Actigall) for liver protection. Patients will also be on antifungal prophylaxis (posaconazole is preferred), antiviral prophylaxis (acyclovir or valacyclovir) and anti-PCP prophylaxis (dapsone, Bactrim).

## 9.6 DEFINITIONS OF DOSE LIMITING TOXICITY

Dose limiting toxicity would be development of Grade 3-4 GVHD. GVHD will be graded according to the Glucksberg criteria.

Dose-limiting toxicity is defined as:

- Grade 3-4 Acute GVHD
- Any Grade 3-4 non-hematologic toxicity related to Daratumumab
- Hematologic toxicity: grade 4 toxicity not related to the underlying disease and not responding to growth factor or transfusion within 7 days

Date of protocol: 10/14/2020

IRB Approval Date: 11/24/2020

Version of protocol: 7

IND number: 139015

Institutional protocol number: OSU 17102

Grade 3 or higher non-neurologic immune-related adverse events (e.g. diarrhea, pruritus, rash) that respond to corticosteroids and improve to grade 1 or less within 4 weeks will NOT count as DLTs. Optional biopsy of affected organs will be encouraged to help determine whether the immune-related condition is due to GVHD. Once a patient develops Grade 3-4 GVHD, further enrollment will be on hold until safety and monitoring committee assesses toxicity.

For patients developing Grade 2 GVHD, further doses of Daratumumab will be held until GVHD is controlled. Patients have to meet above-listed criteria before they can resume Daratumumab.

In the phase II expansion part of the study, if >2 patients develop  $\geq$  Grade 3 GVHD, we will stop enrollment and reassess safety.

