Date of protocol: 10/14/2020

IRB Approval Date: 11/24/2020

Version of protocol: 7

IND number: 139015

Institutional protocol number: OSU 17102

DLT definition	

• Acute GVHD <math>\geq</math> Grade 3

• Any non-hematologic toxicity <math>\geq</math> Grade 3 related to Daratumumab

• Hematologic toxicity: grade 4 toxicity not related to the underlying disease and not responding to growth factor or transfusion within 7 days

• Grade 3 or higher non-neurologic immune-related adverse events (e.g. diarrhea, pruritus, rash) that responds to corticosteroids and improve to grade 1 or less within 4 weeks will NOT count as DLTs. Optional biopsy of affected organs will be encouraged to help determine whether the immune-related condition is due to GVHD

Enrollment schedule	
Dose level 1: Weekly Dara for eight doses; if no infusional toxicity observed or GVHD observed, proceed to next dose level. 3 patients at a time can be enrolled in one dose level.
 
If no GVHD is observed after at least 2 weeks after DLI, enrollment will proceed to next dose level.

Definitions for safety-evaluability	Received at least one dose of Daratumumab
Definition for DLT evaluability	
All patients are evaluable for DLT except patients who are unable to receive 3 doses of daratumumab in dose level 1, or 3 doses of daratumumab and DLT for dose levels 2 and 3 due to progression of AML.
 
DLT observation period will be from the first dose of daratumumab till 7 days post 3rd dose of daratumumab (for dose level 1) and from the first dose of daratumumab till at least 4 weeks post DLI (for dose level 2 and 3)

Definitions for efficacy evaluability:	All eligible patients who receive at least one dose of Daratumumab, do not withdraw consent, and are evaluated for response at week 8.
Dose-limiting toxicity:	Grade 3 or 4 GVHD
Special situations	

1. If patients attain response before DLI, there will be three options at the discretion of treating physician :

a. Proceed with DLI

Date of protocol: 10/14/2020

IRB Approval Date: 11/24/2020

Version of protocol: 7

IND number: 139015

Institutional protocol number: OSU 17102

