### 10.3 OTHER CLINICAL EVENTS

For any grade 3-4 non-hematologic event observed, treating physician will determine relatedness as follows:

Related to leukemia

Definitely

Probably

Possibly

Unlikely

Unrelated

Related to transplant

Definitely

Probably

Possibly

Date of protocol: 10/14/2020  
Version of protocol: 7  
IND number: 139015  
Institutional protocol number: OSU 17102

IRB Approval Date: 11/24/2020

- Unlikely
- Unrelated
- Related to Daratumumab – if Yes, fill one of the boxes below
  - Definitely
  - Probably
  - Possibly
  - Unlikely
  - Unrelated
- Related to DLI
  - Definitely
  - Probably
  - Possibly
  - Unlikely
  - Unrelated

Is event expected - Yes or No

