## 16 STATISTICAL CONSIDERATIONS

Study design/Sample size

This is a phase I/II study evaluating the combination of Daratumumab and escalating doses of DLI in patients with relapsed AML or transformed from MDS to AML post allo-HCT. Three dose levels will be used for related sibling donors and unrelated donors respectively.

Study Design: The standard 3+3 design will be applied to determine MTD of donor lymphocyte infusion when given with a fixed dose of Daratumumab. The dose escalation process for related sibling donor and unrelated donor will be conducted concurrently, but separately.

Dose escalation will proceed within each cohort according to the following scheme.

Number of Subjects with DLT at a Given Dose Level	Escalation Decision Rule
0 out of 3	Enter 3 subjects at the next dose level.
1 out of 3	
Enter 3 more subjects at this dose level.
 

• If 0 of these 3 subjects experience DLT, proceed to the next dose level.

• If 1 or more of this group suffer DLT, then dose escalation is stopped, and this dose is declared the maximally administered dose. Three (3)

Date of protocol: 10/14/2020

IRB Approval Date: 11/24/2020

Version of protocol: 7

IND number: 139015

Institutional protocol number: OSU 17102

	additional subjects will be entered at the next lowest dose level if only 3 subjects were treated previously at that dose.
>2	Dose escalation will be stopped. This dose level will be declared the maximally administered dose (highest dose administered). Three (3) additional subjects will be entered at the next lowest dose level if only 3 subjects were treated previously at that dose.
<1 out of 6 at highest dose level below the maximally administered dose	This is generally the recommended maximally tolerated dose.

The MTD will be defined as the highest safely tolerated dose where at most one patient in six experiences DLT during DLT observation period. The DLT observation period is defined as below.

Dose Level	DLT observation period
1	From the first dose of Daratumumab till 7 days post 3 rd dose
2/3	From the first dose of Daratumumab till at least 4 weeks post DLI

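### The four statements of the DLT definition disagree, and none counts a non-GVHD, non-hematologic event attributed only to DLI, the component being escalated

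*Combined protocol and SAP*

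**What the plan says.** Four statements define a DLT.

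- **Synopsis, DLT definition row.** Acute GVHD of grade 3 or higher; "Any non-hematologic toxicity" of grade 3 or higher if related to Daratumumab; and a hematologic criterion.
- **Synopsis, separate dose-limiting toxicity row.** Only "Grade 3 or 4 GVHD".
- **Section 9.6, opening sentence.** Only grade 3-4 GVHD.
- **Section 9.6, list.** "Grade 3-4 Acute GVHD"; "Any Grade 3-4 non-hematologic toxicity related to Daratumumab"; and, for hematologic toxicity, "grade 4 toxicity not related to the underlying disease and not responding to growth factor or transfusion within 7 days".

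Both full lists exempt certain immune-related events that respond to corticosteroids.

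Section 16 states what the count is for: "The standard 3+3 design will be applied to determine MTD of donor lymphocyte infusion when given with a fixed dose of Daratumumab". The MTD is the highest dose at which no more than one patient in six has a DLT. At dose levels 2 and 3 the observation period runs from the first Daratumumab dose until at least four weeks after DLI. Section 10.3 and the adverse event form in the Appendix record attribution to disease, transplant, Daratumumab and DLI separately.

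**The concern.** A 3+3 design is driven entirely by its DLT count, so the event that is counted has to be defined once and has to reflect the component whose dose changes. Neither holds here.

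First, a team using the synopsis list and a team using the 9.6 list would classify a Daratumumab-related, non-hematologic death differently. A team using either GVHD-only statement would count no other toxicity at all.

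Second, Daratumumab is given at the same dose at every level, and only DLI changes between levels 2 and 3. Yet a non-hematologic event other than GVHD counts only if it is related to Daratumumab. The observation window extends past DLI in order to see what DLI does, but the criterion discards one class of what it may see.

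At stake is the DLI dose declared tolerable, which is then carried into phase II.

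**Working it through.** **Step 1. Apply the four statements to the same events.** Assume each event falls in the observation period and is not covered by the immune-related exemption.

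| Event | Synopsis list | Synopsis second row | 9.6 opening sentence | 9.6 list |
|---|---|---|---|---|
| Grade 3-4 acute GVHD | counts | counts | counts | counts |
| Grade 4 hematologic, not disease-related, not responding in 7 days | counts | no | no | counts |
| Grade 3-4 non-hematologic, related to Daratumumab | counts | no | no | counts |
| Grade 5 non-hematologic, related to Daratumumab | counts | no | no | no |
| Grade 3-4 non-hematologic, not GVHD, attributed to DLI only | no | no | no | no |

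Only the first row is treated alike and counted everywhere. The next three rows are contradictions between passages. The last row is a gap common to all four. Dose level 1 contains no DLI, so that gap can operate only at levels 2 and 3; the grade 5 contradiction can arise at any level.

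**Step 2. Check whether any stated figure depends on the wording.** Section 16 gives 3 to 18 evaluable patients per donor cohort and assumes 10% unevaluable. 3/0.9 = 3.33, rounded up to 4, and 18/0.9 = 20. The stated 4 to 20 is reproduced, and it does not depend on how a DLT is defined.

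**Step 3. Effect on the count.** Under the section 16 table, one event left out turns 1/3 (add three patients) into 0/3 (escalate). It can also turn 2/6 (stop) into 1/6, which permits escalation or fits the MTD definition.

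**Step 4. Illustration of the effect on escalation.** Let T be the true rate of DLT-type events and s the share of them left uncounted, so that the counted rate is p = T(1 − s). The plan escalates after 0/3, or after 1/3 followed by 0/3:

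P(escalate) = (1 − p)³ + 3p(1 − p)² × (1 − p)³

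For T = 0.30 and s = 0: 0.343 + 0.441 × 0.343 = 0.494. For T = 0.30 and s = 0.10, p = 0.27: 0.389 + 0.432 × 0.389 = 0.557.

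| True rate T | all counted | 10% uncounted | 25% uncounted | 50% uncounted |
|---|---|---|---|---|
| 20% | 0.709 | 0.752 | 0.814 | 0.906 |
| 30% | 0.494 | 0.557 | 0.654 | 0.814 |
| 40% | 0.309 | 0.378 | 0.494 | 0.709 |
| 50% | 0.172 | 0.234 | 0.351 | 0.600 |

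Every T and s here is assumed; the documents give neither. With 10% uncounted, the chance of escalating rises by about 4 to 7 percentage points. Across the whole grid the rise is about 4 to 43 points, but nothing in the documents supports the larger shares.

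**The case against.** The case on the other side has real force on scope.

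- **DLI toxicity is not ignored.** A reader might infer that section 9.6 leaves out DLI toxicity altogether. It does not. Its first criterion is grade 3-4 acute GVHD, with no attribution required, and GVHD is the DLI risk that section 4.4 names. The hematologic criterion excludes only disease-related events, so a DLI-related cytopenia can count.
- **The remaining gap may be small.** DLI is given within 72 hours of a Daratumumab dose. Relatedness is scored separately for each agent, with a middle category for possible relation, so many events may be judged related to both. The protocol does not say which category counts as related.
- **Deaths are not excluded by design.** A reader might infer a decision to leave fatal events out of the count. The synopsis list includes them, and 9.6 itself speaks of grade 3 or higher in its immune-related exemption and its phase II rule. This looks like loose drafting. GVHD is graded I to IV in section 8.2, so the 3-4 range omits no severe GVHD.
- **Grade 5 attribution can be recorded.** A reader might infer the contrary from section 10.3: "For any grade 3-4 non-hematologic event observed, treating physician will determine relatedness as follows". But the adverse event form in the Appendix has fields for grade, attribution including DLI, and DLT status, with no grade limit. Section 13.6 also asks for the relationship to the company's product for every adverse event. No change to the 10.3 form is needed.
- **A severe event would not pass unseen.** Section 13.3 makes every death an SAE, section 14.1 sets weekly safety calls, and section 16.3 sets a review after the third patient's DLT window.

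These points narrow the issue to what is stated here. They do not remove it, because SAE reports and calls do not alter the formal count, and the enrollment hold in 9.6 and the committee decision in 14.1 are both written around GVHD.

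**Conclusion.** The point holds in two limited parts. The four DLT statements contradict each other on grade and on whether anything other than GVHD counts. In addition, both full lists tie non-hematologic toxicity to the fixed agent, so a non-GVHD, non-hematologic event attributed only to DLI does not enter the count that sets the DLI MTD. Acute GVHD and hematologic DLTs are unaffected by this second part.

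The conclusion rests on reading the criteria as written. Its practical size cannot be stated, because the documents give no DLT rate and no share of events attributed to DLI alone. The escalation probabilities show direction only. A reader might infer from them that the declared MTD will be materially too high; the documents do not support that, and the upper end of the range should not be used to judge importance. What can be said is that a single uncounted event can reverse a decision made on three or six patients. This should be corrected, since it concerns the phase I primary endpoint and the remedy is cheap.

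**What to change.** Reconcile all four statements (both synopsis rows, the opening sentence of 9.6 and the 9.6 list) into one DLT definition, and have section 16 use that definition for the 3+3 count. Editing the two lists alone would leave the GVHD-only statements in contradiction. The single definition should:

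- state explicitly whether grade 5 events count; and
- cover non-hematologic toxicity attributed to DLI, the escalated component, as well as to Daratumumab, using the attribution already collected under section 10.3 and on the adverse event form.

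The cost is protocol wording. No new data field is needed, and the planned accrual of 4 to 20 per cohort does not change. The downside is that slightly more events may count as DLTs, so escalation may stop somewhat more often.

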## 10 MANAGEMENT OF CLINICAL EVENTS

### 10.1 CYTOPENIAS

Bone marrow biopsies will be done at time of consent, prior to DLI and at week 8. Additional Bone marrow biopsies can be done at any time at discretion of treating physician. If bone marrow shows persistent disease, cytopenias would be attributed to persistent leukemia.

Transfusions will follow institutional guidelines which typically are to keep Hgb > 7gm/dL and platelet (PLT) count more than 10K/ $\mu$ l.

### 10.2 GRAFT VERSUS HOST DISEASE

Patients will be assessed for GVHD at every visit, for new diagnosis of suspected GVHD, biopsy will be done whenever feasible. Management of GVHD will follow guidelines listed in the Programmatic approach to management of GVHD followed at the James.

### 10.3 OTHER CLINICAL EVENTS

For any grade 3-4 non-hematologic event observed, treating physician will determine relatedness as follows:

Related to leukemia

Definitely

Probably

Possibly

Unlikely

Unrelated

Related to transplant

Definitely

Probably

Possibly

Date of protocol: 10/14/2020  
Version of protocol: 7  
IND number: 139015  
Institutional protocol number: OSU 17102

IRB Approval Date: 11/24/2020

- Unlikely
- Unrelated
- Related to Daratumumab – if Yes, fill one of the boxes below
  - Definitely
  - Probably
  - Possibly
  - Unlikely
  - Unrelated
- Related to DLI
  - Definitely
  - Probably
  - Possibly
  - Unlikely
  - Unrelated

Is event expected - Yes or No

## 11 DESCRIPTION OF INVESTIGATIONAL AGENT

### 11.1 STORAGE, HANDLING AND ACCOUNTABILITY

Daratumumab is a colorless to pale yellow, preservative-free solution for intravenous infusion supplied as:

NDC 57894-502-05 contains one 100 mg/5 mL single-dose vial

NDC 57894-502-20 contains one 400 mg/20 mL single-dose vial

#### Storage and Stability

Store in a refrigerator at 2°C to 8°C (36°F to 46°F). Do not freeze or shake. Protect from light. This product contains no preservative.

### 11.2 SAFETY INFORMATION FOR DARATUMUMAB

Daratumumab is a CD38-directed cytolytic antibody that is FDA approved for multiple myeloma. Safety information was obtained from the package insert

(<https://www.darzalexhcp.com/shared/product/darzalex/darzalex-prescribing-information.pdf> and shown below:

1. Infusion reactions: Interrupt Daratumumab infusion for infusion reactions of any severity. Permanently discontinue the infusion in case of life-threatening infusion reactions.

Date of protocol: 10/14/2020  
Version of protocol: 7  
IND number: 139015  
Institutional protocol number: OSU 17102

IRB Approval Date: 11/24/2020

2. Interference with cross-matching and red blood cell antibody screening: Type and screen patients prior to starting treatment. Inform blood banks that a patient has received Daratumumab
3. Neutropenia: Monitor complete blood cell counts periodically during treatment. Monitor patients with neutropenia for signs of infection. Dose delay may be required to allow recovery of neutrophils.
4. Thrombocytopenia: Monitor complete blood cell counts periodically during treatment. Dose delay may be required to allow recovery of platelets.

The most frequently reported adverse reactions (incidence  $\geq 20\%$ ) in clinical trials were: infusion reactions, neutropenia, thrombocytopenia, fatigue, nausea, diarrhea, muscle spasms, back pain, pyrexia, cough, dyspnea, peripheral edema, peripheral sensory neuropathy and upper respiratory tract infection

Patients with AML or MDS transformed to AML have pre-existing thrombocytopenia and neutropenia; abnormalities in blood counts will be attributed to underlying disease.

The effects of Daratumumab on the developing fetus/embryo is not known. Patients will be counselled to use effective contraception methods after transplant and specifically during the time period of study participation and study follow-up.

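### Section 11.2 assigns blood-count abnormalities to the underlying disease without condition, which conflicts with Section 10.1 and, applied as written, would empty the hematologic DLT criterion

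*Combined protocol and SAP*

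**What the plan says.** Four places in the protocol bear on whether a low blood count can be a dose-limiting toxicity.

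- **Section 9.6** lists as a DLT: "Hematologic toxicity: grade 4 toxicity not related to the underlying disease and not responding to growth factor or transfusion within 7 days". The synopsis carries the same criterion: "grade 4 toxicity not related to the underlying disease and not responding to growth factor or transfusion within 7 days".
- **Section 10.1** gives an attribution rule that depends on the marrow: "If bone marrow shows persistent disease, cytopenias would be attributed to persistent leukemia". On timing it says: "Bone marrow biopsies will be done at time of consent, prior to DLI and at week 8". Further marrows are at the physician's discretion.
- **Section 11.2**, in the description of the drug, gives a reason, "Patients with AML or MDS transformed to AML have pre-existing thrombocytopenia and neutropenia", and then the rule: "abnormalities in blood counts will be attributed to underlying disease". The rule has no qualifier for grade, onset, baseline count or marrow result. The same section says that the adverse reactions most often reported (incidence at least 20%) "in clinical trials were: infusion reactions, neutropenia, thrombocytopenia, fatigue, nausea", with others following.
- **Section 10.3** provides a relatedness grid, but limits it: "For any grade 3-4 non-hematologic event observed, treating physician will determine relatedness as follows".

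Section 13.6 separately asks the investigator for a causality opinion on every adverse event, with no exception for hematologic events. Section 16 uses the DLT counts for the 3+3 decisions and for the MTD, which allows no more than one DLT among six patients.

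**The concern.** The hematologic DLT depends on one judgment: whether the event is related to the underlying disease. Section 11.2 appears to settle that judgment in advance for every count abnormality, and always in the direction that stops the event from counting. Section 10.1 settles it in advance only for patients whose marrow still shows disease. No section says which of the two an adjudicator should use in the DLT window, and the grid in Section 10.3 does not help because it leaves out hematologic events.

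At stake is the phase I primary endpoint. Each 3+3 decision rests on three or six patients, so the classification of one event can decide whether escalation continues and which dose of donor lymphocytes goes into phase II. Neutropenia and thrombocytopenia are also among the drug reactions that Section 11.2 itself lists as common, so the event type in question is not a remote one.

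**Working it through.** The plan states no rate of hematologic DLTs, so there is no figure of its own to reproduce. The main check is to run the same event through the competing rules.

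**Step 1: the rules side by side.** Take a grade 4 thrombocytopenia that has not responded after 7 days.

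| Marrow finding | Under 11.2 | Under 10.1 | DLT under 9.6? |
|---|---|---|---|
| Persistent disease | Disease | Leukemia | No under either rule |
| No persistent disease | Disease | Not automatically leukemia | No under 11.2; possible under 10.1 |

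The rules part only in the second row. Under 11.2 the condition of being unrelated to the disease fails for every count abnormality, so the count-based part of the criterion is empty. Under 10.1 it is not.

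**Step 2: can the second row occur?** The protocol provides for it. Patients with MRD only may enroll once the DLT period of dose level 1 is complete (Section 7.1), so they can be treated at the levels that add donor lymphocytes. The synopsis also provides for patients who respond before the infusion. How often such a patient would have a qualifying grade 4 event is not stated.

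**Step 3: can one event change a decision?** Section 16 escalates after 0 of 3, or after 1 of 3 followed by 0 of 3, and stops when the second group of three has a DLT. Suppose six patients at a level have one other DLT, in the first three, and a patient in the second three has the event in the second row. Under 11.2 the count is 1 of 6 and escalation proceeds. Under 10.1, if the event is judged unrelated to disease, it is 2 of 6 and escalation stops.

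**Step 4: illustration of size. All rates are assumed.** Let *o* be the rate of other DLTs and *h* the rate of hematologic events that would count under a reconciled rule. The two are taken as independent.

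- Total DLT rate: p = 1 − (1 − o)(1 − h)
- Chance of escalating past a level: E(p) = (1 − p)³ + 3p(1 − p)⁵

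For o = 0.20 and h = 0.10, p = 1 − 0.80 × 0.90 = 0.28 and E = 0.373 + 0.163 = 0.536. If hematologic events never count, p = 0.20 and E = 0.512 + 0.197 = 0.709.

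| o | h | p | E, counted | E, never counted |
|---|---|---|---|---|
| 10% | 10% | 0.19 | 0.730 | 0.906 |
| 10% | 20% | 0.28 | 0.536 | 0.906 |
| 10% | 30% | 0.37 | 0.360 | 0.906 |
| 20% | 10% | 0.28 | 0.536 | 0.709 |
| 20% | 20% | 0.36 | 0.378 | 0.709 |
| 20% | 30% | 0.44 | 0.248 | 0.709 |

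Here *h* is not the rate of all grade 4 cytopenias. Under 10.1, events with persistent marrow disease would still not count. As *h* approaches zero, so does the difference.

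**The case against.** The best defense is that Section 11.2 is drug information, not a DLT rule. The sentence follows package-insert text and rests on pre-existing cytopenia, so it can be read as covering only abnormalities already present at entry. Both DLT definitions keep the hematologic criterion, which suggests that the authors expected it to operate. Section 10.1, under management of clinical events, is the more natural source for an attribution rule. In strict logic it does not even contradict 11.2, since it is silent on cytopenia without marrow disease. Section 13.6 and the adverse event form, which has attribution and DLT columns, both call for judgment event by event.

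Much of this stands, and it rules out two inferences that a reader might draw.

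- *That the hematologic DLT can never be met.* This would need 11.2 to take precedence, and no section gives it that. Sections 10.1 and 13.6 leave a route.
- *That the safety tables would understate hematologic toxicity.* Section 16.2 tabulates worst-grade events whatever their attribution, and Section 13 makes cytopenias of grade 4 or higher events of special interest. Only the attribution breakdown could shift.

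The defense does not remove the conflict. The sentence in 11.2 is not limited to pre-existing abnormalities in its own words. The marrow condition in 10.1 has no purpose if every count abnormality is assigned to disease anyway. The causality opinion in 13.6 is hard to square with an attribution fixed in advance.

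**Conclusion.** The concern holds as an internal conflict. Section 11.2 is unconditional, Section 10.1 is conditional, and the DLT definition depends on the answer. Applied as written, 11.2 leaves no count-based event that can qualify as a DLT; under 10.1 some can. The disagreement is confined to grade 4 events, unresponsive at 7 days, in patients whose marrow does not show persistent disease.

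Its size is unknown. A reader might take a swing such as 0.454 to 0.709 in the chance of escalation (20% other DLTs, with and without 15% hematologic DLTs; p = 1 − 0.80 × 0.85 = 0.32 against 0.20) as the effect of this conflict. The documents do not support that. The rates and their independence are assumed, and the comparison treats all of the 15% as countable once the text is corrected, although 10.1 would still exclude events with persistent marrow disease. What can be said without assumed rates is that one event classified differently is enough to change a 3+3 decision. The phase II response rule is not affected.

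**What to change.** Reconcile Sections 11.2, 10.1 and 9.6 and the synopsis.

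- Remove the unconditional sentence in 11.2, or qualify it so that it no longer decides DLT attribution.
- State one attribution rule for hematologic events in the DLT window, and refer to it from each place. The clinical content of that rule is for the investigators to decide. It should leave the hematologic criterion able to operate and should agree with the event-level causality opinion required by Section 13.6.
- If the rule relies on the marrow, say which result applies, since marrows are scheduled only at consent, before the lymphocyte infusion and at week 8.
- Say whether the relatedness grid in Section 10.3 covers hematologic events in the window.

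The cost is a short text amendment. Blood counts before each dose and the scheduled marrows are already in the protocol. The downside is that slightly more events may be assessed as DLTs, which could slow or stop escalation at a level where it would otherwise have continued.
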